9.7.2 Descriptive Statistics

Categorical variables will be described by means of absolute and relative frequencies, while continuous variables by means of mean, standard deviation, quartiles, min and max.

Analysis will consider data collected at available observational point, according to clinical practice and clinical judgment. In order to summarise data by time point (e.g. one year after baseline, two years after baseline, etc.), the nearest available evaluation/measurement will be considered (acceptable range).

The clinical features of all patients who switch on-to, or off, Lamzede treatment will be described, including outcomes (efficacy and harms) before switching, reasons for switching, and outcomes (efficacy and harms) after switching. Any patients who switch multiple times will have each switching episode described individually, as well as an overview of that patient's whole experiences.

9.7.3 Patient Demographics and Baseline characteristics

Demographic and baseline characteristics will be summarized by means of descriptive statistics and frequency distributions, as appropriate. The following variables will be presented: age, gender, ethnicity, height, weight, head circumference, rate of growth, Body Mass Index (BMI), alphamannosidosis history (time to diagnosis, time to manifestations, previous infections/fractures, blood genotype results, serum/leukocyte determination of disease activity level, residual enzymatic activity, occurrence of bone marrow transplantation and outcome, hepatic or renal insufficiency), medical history, concomitant disease, previous and concomitant medications including Lamzede received in hospital or home infusion settings, previous and concomitant procedures.

9.7.4 Effectiveness Variables

Effectiveness will be assessed by:

• Oligosaccharides in serum (µmol/L)

Clinical Protocol Number: CLI-LMZYMAA1-12

Clinical Protocol Version Number: 8.0

- 3MSCT (step/min)
- 6MWT (m)
- 2MWT (m)
- FVC (as litre and as percentage of predicted)
- EQ-5D-5L
- Zarit Burden Interview
- CHAQ
- Rate and length of infections (requiring or not antibiotic)
- Serum IgG, IgA and IgM
- Rate of psychotic events
- Behavior Checklists: CBCL prescholar (1.5-5) and scholar (6-18); Adult Behavior Checklist (19-59)/ASR, Older Adult Behavior Checklist (60-and above).

All effectiveness variables will be summarised by means of descriptive statistics or frequency distribution, as appropriate. All variables (actual values and change from baseline, if applicable) will be presented by time point. In addition, mean and individual profiles by time will be produced.

Since alpha-mannosidosis presents as a multi-systemic disease, characterized by many clinical manifestations, a Global Treatment Response (GTR) will be evaluated by aggregating single endpoints in 3 disease relevant domains: pharmacodynamics (reduction of serum oligosaccharides), functional (3MSCT, 6MWT and FVC % of predicted) and quality of life (improvement in CHAQ Disability Index and VAS pain). Patients will be considered responders in one domain if the Minimal Clinical Important Difference (MCID) established for each endpoint from proxy diseases will exceeded in at least one endpoint of the domain; GTR will be reached by patients responding in at least 2 domains.

At the time of planning this registry, adopted MCID are: oligosaccharides below 4 umol/L, increase of 7 steps/minute for 3MSCT (proxy: MPS IV A), increase of 30 meters for 6MWT (proxy: Pompe disease), increase of 10% for FVC (proxy: Pompe disease), decrease of 0.13 for CHAQ DI (proxy: Juvenile Arthritis) and of 8.2% for CHAQ pain (as in paediatric rheumatology). However, taking into account the length of this registry and the disease characteristics, if new scientific factors (i.e. knowledge about alpha-mannosidosis, clinical guidance) emerge the criteria used to establish the GTR may be reviewed and additional criteria may be added (like, but not limited to, EQ-5D-5L and serum IgG). The Global Treatment Response rate after 3 years of Lamzede treatment in naïve patients able to perform the functional tests will be evaluated. The proportion of responders and the corresponding exact (Clopper-Pearson) two-sided 95% confidence interval (CI) will be presented.

Effects of baseline characteristics will be evaluated by means of regression/logistic models including:

- age subgroup (<18 years, \geq 18 years),
- gender (male, female),
- genotype by subcellular localization of the protein (Genotype Group 1, Genotype Group 2, Genotype Group 3, as defined by Borgwardt et all., 2015)
- baseline residual enzymatic activity (<10 nmol/h/mg, 10 to <15 nmol/h/mg, \geq 15 nmol/h/mg)
- baseline CHAQ Disability Index (0|-|1, 1-|2, 2-|3)

as covariates.

Clinical Protocol Number: CLI-LMZYMAA1-12	
Clinical Protocol Version Number: 8.0	Date: 01 February 2019

Comparison with control group will be done descriptively, provided that a minimum number of nontreated patients with adequate data will be enrolled. If data will allow, Global Treatment Response after 3 year will be analysed comparing the two groups using propensity score (PS) analysis. The PS will be calculated as the predicted probability of Lamzede-treated vs non-treated patients from a logistic regression. This score represents the "propensity" for an observation to be in a treatment group or the other. The logistic regression model will include the following confounding factors as explanatory variables:

- age subgroup (<18 years, \geq 18 years),
- gender (male, female),
- genotype by subcellular localization of the protein (Genotype Group 1, Genotype Group 2, Genotype Group 3, as defined by Borgwardt et all., 2015)
- baseline residual enzymatic activity (<10 nmol/h/mg, 10 to <15 nmol/h/mg, \geq 15 nmol/h/mg)
- baseline CHAQ Disability Index (0-1, 1-2, 2-3)

The distributions of each confounding factor as well as of the calculated PSs (Lamzede-treated vs non-treated) will be displayed graphically for both groups and their similarity evaluated.

In addition, depending on the outcome of interest and available sample size, subgroup analyses may be performed and results will be presented and regarded as descriptive. Further exploratory analyses will be developed as necessary and fully described in the SAP.

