Variables:	 discretion of the Investigator. Effectiveness Variables Effectiveness will be assessed by: Oligosaccharides in serum (µmol/L) 3-Minute Stair Climb Test (3MSCT) (step/min) 6-Minute Walk Test (6MWT) (m) 2-Minute Walk Test (2MWT) (m) Forced Vital Capacity (FVC) (as litre and as percentage of predicted) EQ-5D-5L Zarit Burden Interview Childhood Health Assessment Questionnaire (CHAQ) Rate and length of infection (requiring or not antibiotic) Serum IgG, IgA and IgM Rate of psychotic events Behaviour Checklists (Childhood, Adult and Older Adult) In patients below 4 years of age, 3MSCT, 2MWT and FVC % of predicted will be proposed upon the judgment of the treating physician. Since alpha-mannosidosis presents as a multi-systemic disease, characterized by many clinical manifestations, a Global Treatment Response (GTR) will be evaluated by aggregating single endpoints in 3 disease relevant domains: pharmacodynamics (reduction of serum oligosaccharides), functional (3MSCT, 6MWT and FVC % of predicted) and quality of life (improvement in CHAQ Disability Index and VAS pain). Clinically significant response assigned to each domain when at least one parameter of the domain will be improving beyond the proposed Minimal Clinical Important Difference (MCID) established for each 	
	endpoint from proxy diseases. Patients will then be qualified as a GTR-responder if the response criteria was reached in at least two domains. Global Treatment Response rate after 3 years of Lamzede treatment in naïve patients able to perform the functional tests will be evaluated.	
	 Safety Variables Safety will be assessed by: Adverse Events (AEs) including non-serious and Serious AEs, including non-serious and serious adverse drug reactions (ADRs), AEs leading to treatment discontinuation and AEs leading to death at any time they become available. anti-velmanase alfa-IgG antibody (ADA), infusion related reactions (IRRs) and hypersensitivity (as identified risks) 	

Clinical Protocol Number	: CLI-LMZYMAA1-12
--------------------------	-------------------

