- 7. All assessments mentioned in the above table will be collected only if considered necessary and available as part of routine clinical practice by the treating physician and no additional tests specific to the Registry will be done.
 - 7a. The markers (oligosaccharides in serum, IgG, IgA and ADA) will not be evaluated by a central laboratory for German patients only, while markers testing will take place according to local routine clinical practice in Germany.
- The markers oligosaccharides in serum, IgG, IgA and ADA) will be evaluated through a central laboratory in EU countries other than Germany.
- 8. Standardtest for haematology and chemistry assessed by local laboratory if available per clinical practice of the site:
 - a. Haemoglobin, haematocrit, platelet count, red blood cells, white blood cells with differential count (band forms, segment forms, neutrophils, eosinophils, basophils, monocytes, lymphocytes) (all expressed in % as well as in absolute numbers). Blood smear for leukocytes detection by electronic microscopy may be done at the treating physician's discretion.
 - b. Biochemistry: Serum electrolytes (sodium, potassium, calcium, inorganic phosphate), creatinine, creatinekinase, amylase, AST, ALT, ALP, albumin, bilirubin (total and direct), LDH.
- 9. In patients from 4 years of age and when applicable according to the judgment of treating physician.
- 10. In patients *below* 4 years of age and when applicable according to the judgment of treating physician.
- 11. Adverse Events /Adverse Drug Reactions based on all risk categories associated with Lamzede EU RMP, including infusion related reactions (IRRs) and hypersensitivity (as identified risks), acute renal failure, loss of consciousness and medication errors (as potential risks). Data on pregnancy and lactation (as missing information) will be also collected if available.
- 12. One of the Behavior Checklists (CBCL prescholar-scholar, ABCL/ASR (self-reporting), OABCL) will be used to the applicable age and according to the judgment of treating physician.

9.3 Variables

Only available evaluations as decided by the treating physician based on local routine clinical practice will be collected in the Registry. Patients' retrospective data may be collected if available. Where there are no data to report, this will be indicated in the applicable section(s) of the eCRF. See Table 1 for the schedule of assessments to be reported.

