Functional tests included in the Global Treatment Response (GTR) (namely 3MSCT, 6MWT, EQ-5D-5L and FVC are considered not doable in very young paediatric patients (i.e. < 4 years), due to the subject's inability to adequately execute the tests. Therefore, pre-treatment data will not be collected in this population (limited to these tests) in the infrequent case of patients starting treatment

Clinical Protocol Number: CLI-LMZYMAA1-12

Clinical Protocol Version Number: 8.0	Date: 01 February 2019

before 4 years Concerning the 2MWT will be eventually performed according to the judgment of the treating physician For non-treated patients who are enrolled at such young age, but start treatment later, it will be strongly advised to the treating physician to take care of the fact that at least one pre-treatment battery of motor function tests is performed.

*Serum oligosaccharides, serum IgG, IgM and IgA, anti-velmanase alfa-IgG antibody (ADA) will be assessed by a centralised and specialised laboratory. In Germany these markers will not be evaluated by the central laboratory, but theywill be evaluated for German patients only locally in accordance to German requirements as part of routine clinical practice.

This centralised evaluation is needed to perform the quantitative detection by validated and consistent methods of the mentioned biochemical parameters, as specialised laboratories in these specific determination might be not locally available yet or some variability among different laboratories might introduce at certain extent limits in results' comparability. The MAH reassures that patients will not be undergoing additional or other than routine testing based on inclusion into the registry and that the testing within the Registry will only take place as part of routine clinical practice.

On the other hand, the MAH is not in the position, as per current rules, to offer the collection of serum samples for the testing of serum oligosaccharides, IgG, IgM and IgA and ADA as part of general clinical practice to patients treated with velmanase alfa who are not willing to participate in the registry and who are not signing the relevant informed consent form prior to any study related procedures and data collection.

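### The pharmacodynamic domain of GTR is described as a reduction but scored as a level below 4 umol/L with no baseline condition, and one cut-off serves both central and German local laboratories

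*Protocol*

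**What the plan says.** Section 9.7.4 of the protocol builds GTR from three domains and names the first as "pharmacodynamics (reduction of serum oligosaccharides". A domain counts when the minimal clinically important difference (MCID) "will exceeded in at least one endpoint of the domain", and "GTR will be reached by patients responding in at least 2 domains". The abstract (section 4, Variables) uses the language of change too: a domain responds when "at least one parameter of the domain will be improving beyond the proposed" MCID.

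The same section then gives the working thresholds: "adopted MCID are: oligosaccharides below 4 umol/L, increase of 7 steps/minute for 3MSCT". The rest of the list sets increases for the 6MWT and FVC and decreases for the CHAQ Disability Index and CHAQ pain. Oligosaccharides are the only endpoint in the PD domain.

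On measurement, 9.3.3 justifies central testing partly because "some variability among different laboratories might introduce at certain extent limits" to comparability of results. Footnote 7a of Table 1 (9.2.6) states that oligosaccharides and the other markers "will not be evaluated by a central laboratory for German patients only"; they are tested locally there.

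**The concern.** An MCID is a difference, but this criterion contains none. It asks only where the patient is on treatment, not where the patient started. Nothing else in the protocol supplies the missing condition. Section 9.2.3 has no exclusion criteria, and 9.7.4 restricts the GTR analysis only to naive patients able to perform the functional tests. No minimum pre-treatment oligosaccharide value is stated.

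This bears on the primary effectiveness measure. GTR needs two of three domains. A patient who holds the PD domain by starting level then needs one pass among five parameters (three functional, two quality of life).

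A fixed level also carries any difference between laboratories straight into responder status. The protocol itself warns of such differences, then applies one number to both sources and states no harmonisation rule.

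**Working it through.** **1. The criteria side by side (9.7.4).**

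| Endpoint | Criterion | Uses baseline? |
|---|---|---|
| Serum oligosaccharides | below 4 umol/L | no |
| 3MSCT | increase of 7 steps/min | yes |
| 6MWT | increase of 30 m | yes |
| FVC | increase of 10% | yes |
| CHAQ Disability Index | decrease of 0.13 | yes |
| CHAQ pain | decrease of 8.2% | yes |

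One criterion of six has no change term, and it alone decides the PD domain. Under the literal rule, a patient at 3 umol/L before and after treatment is a PD responder, and so is one who rises from 3 to 3.5. These values are invented to show the rule.

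**2. The plan's own figure (9.5).** Inputs: n = 70, exact Clopper-Pearson, two-sided 95%. With x = 70 × 0.60 = 42, the interval is 0.476 to 0.715, width 0.239, as printed. All five rows of the table reproduce to three decimals. No printed figure is wrong.

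**3. What unearned PD credit does to GTR.** Let F and Q be the probabilities of functional and quality-of-life response, assumed independent.

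- Without PD credit, GTR requires both: F × Q.
- With PD credit, GTR requires either: F + Q − F × Q.
- Gain per credited patient: F + Q − 2FQ, the probability of passing exactly one.

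| F = Q | Without credit | With credit | Gain |
|---|---|---|---|
| 0.3 | 0.09 | 0.51 | 0.42 |
| 0.5 | 0.25 | 0.75 | 0.50 |
| 0.7 | 0.49 | 0.91 | 0.42 |

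If a share s of patients has unearned credit, GTR rises by s × gain:

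- s = 5%: 2.1 to 2.5 points
- s = 10%: 4.2 to 5.0 points (2.9 to 3.5 of 70 patients)
- s = 20%: 8.4 to 10.0 points

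Unequal probabilities widen this a little: F = 0.7 and Q = 0.3 give 0.7 + 0.3 − 0.42 = 0.58, or 5.8 points per 10%. Positive correlation between the domains makes passing exactly one less likely and so shrinks the gain.

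**4. Against the 45% remark in 9.5.** Exact lower limits at n = 70 are 0.476 for 42 responders, 0.462 for 41 and 0.447 for 40. Two fewer responders in the 0.60 scenario therefore put the limit below 45%. Two excess responders would be expected from about 2/0.50 = 4 to 2/0.42 = 4.8 credited patients, roughly four or five of 70.

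**5. Laboratories.** The protocol gives no assay bias. An assay that reads low can award the domain and one that reads high can deny it, so no direction can be assigned.

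**The case against.** The text has a sensible joint reading: a reduction that ends below 4 umol/L. That may well be the intent, and it limits the repair to one sentence. But 9.7.4 does not say it, and the numerical rule is what will be programmed.

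Nothing shows that affected patients exist. The disease is characterised by accumulation of these oligosaccharides, and restricting GTR to naive patients removes low values caused by earlier Lamzede. Prior bone marrow transplantation is recorded, but no passage links it to values below 4. This objection stands in full as to size; it does not supply the missing condition.

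Four stronger readings are tempting and not supported.

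- A reader might infer that GTR is inflated by some five points. That needs a 10% share and independent domains, neither of which is in the protocol. Deriving domain rates from the 30% placebo GTR in 7.1 does not help: if one assumes no placebo PD response, one also assumes that no placebo patient had free credit under this rule.
- A reader might infer that local assays favour response. The effect can go either way. Local testing follows a German requirement (9.3.3), and 9.9 already lists differences between sites as a limitation.
- A reader might infer that a retrospective baseline from another assay distorts PD response. It cannot, because the current rule has no baseline term.
- A reader might treat 45% as a success criterion. Section 9.5 offers it as a comment on precision, and no hypothesis is tested.

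Low starting values would also show in the individual profiles and changes from baseline that 9.7.4 already plans. That makes the problem visible but leaves the responder count unchanged.

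**Conclusion.** The point holds as an inconsistency in a rule that the protocol itself fixes, so it is not a detail left to the SAP. The PD domain is described as a reduction, scored as a level, and can be credited without any reduction. Applying one absolute cut-off to two laboratory sources adds possible misclassification of unknown direction.

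The mechanism follows from the wording; the size is unknown. The 4 to 5 points per 10% of patients rest on equal, independent functional and quality-of-life domains and an assumed share. The move from 0.476 to 0.447 shows only that a couple of patients matter at n = 70. The change should be made, but nothing here shows that GTR will in fact be biased.

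**What to change.** In 9.7.4, define PD response as a pre-treatment serum oligosaccharide value of at least 4 umol/L falling to below 4 umol/L on treatment. State that patients below 4 at baseline cannot be PD responders and can reach GTR only through the functional and quality-of-life domains. Align the abstract with this.

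Report PD response and GTR by central versus German local laboratory as a sensitivity analysis. The new rule still uses an absolute cut-off, so it does not remove a laboratory offset; this table is what would reveal one.

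Do not count patients without a same-laboratory pair as non-responders. That would turn missing data into failure and bias GTR downwards. At most, add a sensitivity analysis restricted to same-laboratory pairs, which becomes relevant once a baseline value enters the rule.

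The cost is one sentence and one table. A few patients may lose PD-responder status, so GTR may be slightly lower and less directly comparable with the responder analysis of the earlier trials in 7.1.

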8. RESEARCH QUESTION AND OBJECTIVES

Primary Objective

- To assess the long-term effectiveness and safety of treatment with Lamzede under conditions of routine clinical care.
- In terms of effectiveness, the primary focus of the registry is to estimate the Global Treatment Response rate as percentage of patients qualified as responders by aggregately assessing oligosaccharides in serum (umol/L), (GTR-Pharmacodynamic Domain), 3MSCT (step/min), 6MWT (mt), FVC (% of predicted) (GTR-Functional Domain) and QoL based on CHAQ VAS-Pain and CHAQ- Disability Index (GTR-QoL Domain).
- In terms of safety, the rate of AEs (including ADA, IRRs and Hypersensitivity as identified risks) in the treated patients will be the main research of the study.

Secondary Objectives

- To characterize the alpha-mannosidosis population, including clinical manifestation, progression and natural history.
- In particular, oligosaccharides in serum (umol/L), endurance based on 3MSCT (step/min), 6MWT (m) and 2MWT (m) assessment, respiratory function through FVC (as litre and as percentage of predicted), hearing function with PTA, length and rate of infections (requiring or not antibiotics), rate of psychotic events, immunological status as per serum IgG, IgA and IgM, and QoL assessed by EQ-5D-5L, Zarit Burden Interview, CHAQ, Behavior Checklists (prescholar, scholar, adult and older adult) will be adopted for characterizing the alpha-mannosidosis population
- Rate of incidence of acute renal failure and loss of consciousness (as potential risks under Lamzede treatment), change in vital signs (SBP, DBP), laboratory tests (haematology and chemistry), physical examination and ECG will also be monitored.

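### The primary GTR definition may be changed during the registry with results in view, nothing keeps the version 8.0 definition as primary, and added parameters can never lower the rate

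*Protocol*

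**What the plan says.** Section 8 makes GTR the main effectiveness outcome: "the primary focus of the registry is to estimate the Global Treatment Response rate". It names six parameters in three domains: serum oligosaccharides (pharmacodynamic); 3MSCT, 6MWT and FVC % predicted (functional); CHAQ Disability Index and CHAQ VAS pain (quality of life). The Abstract and section 9.7.4 use the same six.

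Under section 9.7.4 a domain responds when the minimal clinically important difference (MCID) is exceeded "in at least one endpoint of the domain; GTR will be reached by patients responding in at least 2 domains". The same section gives the MCIDs as those adopted at planning. It then permits a change: "the criteria used to establish the GTR may be reviewed and additional criteria may be added". The permission depends on new knowledge about the disease or new clinical guidance, and the candidates are given as "like, but not limited to, EQ-5D-5L and serum IgG". It does not say who decides, by what date, whether those deciding may have seen results, or what becomes of the present definition.

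Section 9.6 gives the CRO and the sponsor read access to all sites' data. Section 6 plans a yearly interim report. The ENCePP checklist (Annex 2, section 11) states that no independent review of results is planned. Section 9.5 gives a Clopper-Pearson precision table for 70 treated patients and treats a lower 95% limit above 45% as clinically relevant.

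One sentence elsewhere does not match. Section 9.3.3, on children under 4, says: "Functional tests included in the Global Treatment Response (GTR) (namely 3MSCT, 6MWT, EQ-5D-5L and FVC are considered not doable". No other description of GTR includes EQ-5D-5L.

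**The concern.** The registry is unmasked and its data accumulate in the sponsor's sight. EQ-5D-5L and serum IgG, the two named candidates, are already scheduled and analysed as effectiveness variables, so their effect on the GTR rate could be known before they were added. Because the rule accepts any one passing endpoint, additions push in only one direction.

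Two things are at stake. The primary rate could drift upward through its definition rather than through patient outcomes. And a rate under an amended definition would not match earlier yearly reports, nor the precision table and 45% mark of section 9.5, which were set for the present definition. The study estimates and does not test, so the harm is bias and lost comparability, not type I error.

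**Working it through.** **1. The plan's own figures.** Inputs (section 9.5): N=70, exact two-sided 95% Clopper-Pearson interval. For x responders the limits are the 2.5% quantile of Beta(x, 71−x) and the 97.5% quantile of Beta(x+1, 70−x). With x = 70p:

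| p | x | computed limits | width |
|---|---|---|---|
| 0.60 | 42 | 0.476–0.715 | 0.239 |
| 0.65 | 45.5 | 0.527–0.760 | 0.234 |
| 0.70 | 49 | 0.579–0.804 | 0.225 |
| 0.75 | 52.5 | 0.632–0.846 | 0.214 |
| 0.80 | 56 | 0.687–0.886 | 0.199 |

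All five rows match the protocol.

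**2. Direction of an addition.** Code each parameter 1 if it passes. A domain is the maximum of its parameters, and GTR = 1 if the domain sum is at least 2. Both steps are non-decreasing in every parameter, so a further parameter cannot turn a responder into a non-responder.

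A full enumeration agrees. It covers 2^8 = 256 patterns (six present parameters plus EQ-5D-5L and IgG) under four additions: EQ-5D-5L in the quality-of-life domain; IgG in the pharmacodynamic domain; both; and IgG as a fourth domain with the two-domain rule kept. Over 256 × 4 = 1,024 checks, no responder is lost and 88 non-responders become responders.

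This covers additions only. Tightening an MCID can lower the rate. Requiring 3 of 4 domains loses responders in 3 of the 16 domain patterns and gains none. The denominator is taken as fixed, in line with section 9.7.7, which does not exclude patients with missing values.

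**3. Sensitivity of the 45% mark.** At N=70, 40 responders (57.1%) give a lower limit of 0.447 and 41 (58.6%) give 0.462. One reclassified patient can cross the line. Five (42 to 47) move the interval from 0.476–0.715 to 0.549–0.779.

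**4. Illustrative size.** From the protocol (section 7.1): 30% of placebo patients met the two-domain rule at 12 months, none in all three domains. Assumed: no placebo pharmacodynamic response; functional (F) and quality-of-life (Q) domains equal and independent; one parameter added to the quality-of-life domain and one to the pharmacodynamic domain, each passed by chance with probability q.

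- Start: F = Q = √0.30 = 0.548, so F·Q = 0.30.
- After the additions: Q′ = 1 − (1 − 0.548)(1 − q).
- GTR = F·Q′ + q[F(1 − Q′) + Q′(1 − F)].

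| q | Q′ | GTR | about x/70 | lower 95% limit |
|---|---|---|---|---|
| 0.1 | 0.593 | 0.325 + 0.1 × 0.491 = 0.374 | 26 | 0.26 |
| 0.2 | 0.638 | 0.350 + 0.2 × 0.487 = 0.447 | 31 | 0.32 |
| 0.3 | 0.683 | 0.374 + 0.3 × 0.482 = 0.519 | 36 | 0.39 |

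No lower limit reaches 45%. The equal split matters. Other splits giving 0.30, from F=0.33, Q=0.9 to F=0.9, Q=0.33, yield about 0.37–0.42, 0.43–0.53 and 0.50–0.62 for the three values of q. Only near the top of the last range would the count reach the 41 needed.

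**The case against.** The provision is conditional, not free discretion: it is triggered by new knowledge or clinical guidance. Most MCIDs come from proxy diseases, enrolment is indefinite and each patient is followed for 15 years, so a review clause is understandable. This stands, but it limits the reason for a change, not its timing or what those deciding have already seen.

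The components are also reported individually by time point, and EQ-5D-5L and IgG are scheduled from baseline. A redefinition would therefore be hard to conceal, and a revised rule could be applied backwards where data exist. This too stands. It makes the fix cheap, but the protocol does not commit to such parallel reporting. The SAP could add it, yet the permission to change the primary outcome is in the protocol itself.

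Three stronger readings are tempting and not supported:

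- That chance additions alone bring a no-effect GTR up to the protocol's 45% benchmark. That figure is for the lower confidence limit, not the point estimate; 41 of 70 are needed, and the main illustration gives at most about 36.
- That the definition is already drifting. The same six parameters appear in the Abstract and sections 8 and 9.7.4; section 9.3.3 holds one isolated inconsistency in a sentence about feasibility.
- That a planned comparison with the earlier trials is broken. The 79% and 88% rates in section 7.1 are for 12 months and last observation; the registry rate is at 3 years in naïve patients, and no formal comparison is planned.

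**Conclusion.** The point holds for what section 9.7.4 permits and leaves unprotected: the primary outcome may be redefined with results in view, and the version 8.0 definition need not survive as primary or alongside. The one-directional argument is exact for added parameters while the one-endpoint and two-domain rules and the denominator stay fixed; it does not extend to revised thresholds. The consequence is possible, not certain: upward bias and loss of comparability between yearly reports and with section 9.5.

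The size is illustrative. The single-patient sensitivity at 40 versus 41 responders follows from the protocol's own N and interval. The rise from 30% to about 37–52% rests on assumed pass rates, domain placement, independence and an equal split; section 9.7.4 assigns neither candidate to a domain. A reader should not infer that the sponsor intends to adjust the result; nothing in the protocol suggests it. This should be corrected, but it does not invalidate the design.

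**What to change.** In section 9.7.4, state that the six parameters, thresholds and 2-of-3-domain rule of version 8.0 are the primary GTR in every yearly report and in the final analysis. State that any revised or extended GTR is a separately labelled secondary result, always shown beside the primary one, with the date of the change and the scientific reason for it.

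Reconcile the section 9.3.3 sentence that lists EQ-5D-5L among the GTR tests with the Abstract and sections 8 and 9.7.4, worded so that which tests are collected in children under 4 does not change.

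The cost is a few sentences. No new data are needed, the precision table stands, and new knowledge can still be reported.
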